8.7.2.1 Adverse Events by preferred Terms (AEs/ADRs/SAEs)

All AEs recorded in the CRF will be classified by body organs and terms under the classification standard of MedDRA terms, and all AEs excluding the AEs whose 'Causality' is "Unlikely" will be treated as AEs whose causality cannot be excluded (hereafter "Adverse Drug Reaction (ADR)"). The study database will not be locked until coding is complete.

- The number of AE according to Severity (Mild, Moderate, Severe), Outcome of the event (Recovered, Not yet recovered, Sequelae, Fatal, Unknown), Action taken with trial drug due to AE (Continue, Reduced, Discontinued, Increased, Discontinued and reintroduced, Not applicable), Causality (Certain/ Probable·Likely/ Probable/ Possible/ Unlikely/ Conditional· Unclassified/ Unaccessible·Unclassifiable), Therapy for the event (Yes, No) will be calculated.
- ② All AEs will be classified into the preferred terms according to Severity (Mild, Moderate, Severe), Outcome of the event, (Recovered, Not yet recovered, Sequelae, Fatal, Unknown), Action taken with trial drug due to AE (Continue, Reduced, Discontinued, Increased, Discontinued and reintroduced, Not applicable), Causality (Certain, Probable/Likely, Possible, Unlikely), Therapy for the event (Yes, No). Also, the number of each AE will be calculated.
- The number of patients and the number of Serious AE/Serious ADR (SADR), unexpected AE/ADR, unexpected Serious AE/unexpected Serious ADR, AE/ADR will be calculated according to the preferred terms. Also, the incidence proportion and its 95% confidence interval will be estimated.
- Tor subjects excluded from safety analysis set [‡], the number of patients and the number of Serious AE/Serious ADR (SADR), unexpected AE/unexpected ADR, unexpected Serious AE/unexpected Serious ADR, AE/ADR will be calculated according to the preferred terms. Also, the incidence proportion and its 95% confidence interval will be estimated.

‡Patients excluded from safety analysis sets: 'Patients who have not taken JARDIANCE[®]' and 'Follow-up failure' of patients excluded from safety analysis sets will be excluded (This term reflects the Ministry of Food & Drug Safety (MFDS) guideline).

Safety analyses will be based on all patients treated, i.e. all patients who received at least one dose of JARDIANCE[®] except those who are found to have no observation after enrolment, invalid registration, or invalid contract with the site. However, if data for patients who have been treated with JARDIANCE[®] beyond the scope of approved label are collected, separate

Proprietary confidential information © 2017 Boehringer Ingelheim International GmbH or one or more of its affiliated companies

safety analyses will be performed. Patients lost to follow up will be characterized compared to the remaining patients and reason and time point of loss to follow up will be evaluated.

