8.3.1.3 Number of cases subject to safety evaluation

These include those who signed the informed consent form to participate in this study as subject, took JARDIANCE® once at least, and were followed up by the physician once or more.

Reflecting Ministry of Food & Drug Safety (MFDS) guideline, the cases below shall be excluded from safety analysis (defined below) set in the following order:

- a. Patients who signed on the data release consent form of JARDIANCE® rPMS prior to the contract date
- b. Patients administrated JARDIANCE® prior to the contract date
- c. Patients administrated JARDIANCE® prior to the signed on the data release consent form
- d. Patients who have not taken JARDIANCE®
- e. Follow-up failure: Patients whose safety information can not be obtained due to follow-up Loss
- f. Patients who were prescribed for other indications except indications in the local label

Proprietary confidential information © 2017 Boehringer Ingelheim International GmbH or one or more of its affiliated companies

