10.2 ADVERSE EVENT AND SERIOUS ADVERSE EVENT COLLECTION AND REPORTING

The investigator shall maintain and keep detailed records of all AEs in their patient files.

Collection of AEs

The study design is of non-interventional nature and the study is conducted within the conditions of the approved marketing authorization. Sufficient data from controlled interventional studies are available to support the evidence on the safety and efficacy of the studied JARDIANCE[®]. For this reason the following AE collection and reporting requirements have been defined.

All adverse events occurred from the signing date on ICF to 30 days after last administration date of medication need to be collected, documented and reported to the sponsor using the AE reporting form of eCRF (13.1).

All SAEs, ASAEs and AESIs must be reported with details of relevant non serious AEs, occurring at the same time, within 24 hours of occurrence and via telephone/fax to the Local PV Manager (LPVM) of BI Korea using the NIS AE form (13.2). All non-serious Adverse Reactions associated with JARDIANCE® (empagliflozin) and pregnancy monitoring forms must be reported within 7 calendar days of occurrence and via telephone/fax to the LPVM of BI Korea. If any new or further information to these events is available, a follow-up NIS AE report has to be sent to BI. All SAEs and non-serious AEs must include a causal relationship assessment from the physician.

All ADRs (serious and non-serious), including those persisting after study completion must be followed up until they are resolved, have been sufficiently characterized, or no further information can be obtained.

Contact details:

Local PV Manager (LPVM)

Address: BoehringerIngelheim Korea, Medical Dept. [name]

The investigator carefully assesses whether an AE constitutes an Adverse Reaction using the information below.

Proprietary confidential information © 2017 Boehringer Ingelheim International GmbH or one or more of its affiliated companies

Causal relationship of AEs

The definition of an adverse reaction implies at least a reasonable possibility of a causal relationship between a suspected medicinal product and an AE. An adverse reaction, in contrast to an AE, is characterised by the fact that a causal relationship between a medicinal product and an occurrence is suspected.

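### The adverse-event incidence planned for patients excluded from the safety set pools patients observed from first dose with patients observed only from a later consent date, and its denominator rule is ambiguous

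*Protocol*

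**What the plan says.** Section 8.3.1.3 of the protocol lists six reasons, a to f, for which patients are "excluded from safety analysis (defined below) set in the following order". In short, they are:

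- a: consent was given before the site's contract was dated
- b: treatment began before that contract was dated
- c: treatment began "prior to the signed on the data release consent form"
- d: the drug was never taken
- e: loss to follow-up left no safety information
- f: the prescription was outside the labelled indications

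For patients excluded in this way, section 8.7.2.1 plans counts, an incidence proportion and a 95% CI, by preferred term and by event class (all, serious, unexpected, drug reaction). A footnote removes two groups from this analysis, using the labels of d and e: these groups "of patients excluded from safety analysis sets will be excluded". Groups a, b, c and f remain.

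Section 10.2 sets the collection window: "All adverse events occurred from the signing date on ICF to 30 days after last administration date of medication". It opens at consent, not at first dose.

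**The concern.** An incidence proportion can be interpreted when everyone in its denominator is followed from a comparable starting point and can contribute an event. Two features of this table put that in doubt. Some of the pooled patients were already on treatment when collection of their events began. Others may have no safety information at all and still be counted, depending on how the footnote is read.

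Safety is the primary objective (section 7.1), and reasons a to c remove patients who may well have been treated, on grounds of administrative timing. For them, this table is the planned adverse-event output. A reader who uses it to judge whether those exclusions matter needs to know what its percentage measures.

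**Working it through.** The protocol gives no event rate, no group sizes, no interval from first dose to consent and no loss rate, so there is no planned figure to reproduce. The first step is logic from the text. The later steps illustrate size on assumed inputs.

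**Step 1: who is in each retained group.** The rules are applied in sequence.

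- A patient who reaches b has passed a, so consent is on or after the contract date. First dose is before the contract date, so first dose precedes consent.
- In c, first dose precedes consent by definition.
- A patient who reaches f has passed b, c, d and e, so the patient is treated, was not dosed before consent, and has safety information.

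| Group | First dose before consent | Can lack safety information | Can be untreated |
|---|---|---|---|
| a | possible | yes | yes, on the ordering alone |
| b | always | yes | no |
| c | always | yes | no |
| f | never | no | no |

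With collection starting at consent, on-drug events before consent are outside the window for all of b and c and for part of a.

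**Step 2: effect of late entry.** Assumptions: 20% of patients have an event in the first 24 weeks on drug; the hazard in weeks 0 to 4 is r times the later hazard h; consent comes at week 4; observation then runs 24 weeks; events in separate periods are independent.

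- h = −ln(1 − 0.20) / (4r + 20)
- Observed proportion = 1 − exp(−24h)
- Proportion from first dose to end of observation (28 weeks) = 1 − exp(−h(4r + 24))

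For r = 4: h = 0.2231/36 = 0.00620. Observed is 1 − exp(−0.1488) = 13.8%. From first dose it is 1 − exp(−0.2479) = 22.0%.

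| r | Observed after consent | First 24 weeks on drug | First dose to end of observation |
|---|---|---|---|
| 0.5 | 21.6% | 20.0% | 23.2% |
| 1 | 20.0% | 20.0% | 22.9% |
| 2 | 17.4% | 20.0% | 22.5% |
| 4 | 13.8% | 20.0% | 22.0% |

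Against the last column the observed figure is low in every row. Against the fixed 24-week column it is low if risk is concentrated early, equal if the hazard is constant, and high if early risk is lower. With a gap of one week instead of four, the observed figures are 20.4%, 20.0%, 19.4% and 18.5% for r = 0.5, 1, 2 and 4.

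**Step 3: effect of patients without safety data.** This applies only if the footnote removes the ordered categories d and e. A patient dosed before consent and then lost is classified under c and never reaches e. If a share L of the retained patients has no data, the reported proportion is p(1 − L). For p = 20% this gives 19%, 18% and 16% at L = 5%, 10% and 20%. It cannot raise the figure.

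**Step 4: both together.** With half the group entering late (r = 4, four-week gap) and L = 10%: (0.5 × 13.8% + 0.5 × 20%) × 0.90 = 15.2%, against 20%.

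**The case against.** A reader might infer that the pooled figure is always too low and makes the excluded patients look safer than they are. The documents do not support that. Against a fixed 24-week window, late entry can lower the figure, leave it unchanged or raise it, and the protocol gives no event timing. Nor does the protocol plan a comparison of this table with the safety set, or any conclusion that the exclusions are harmless. This part of the objection stands. What remains is that events between first dose and consent are missing, so incidence counted from first dose is understated.

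The footnote can also be read as removing anyone who is untreated or lost, whichever reason excluded them first. Section 8.3.1.3 does not say that a patient carries only the first matching label into section 8.7.2.1. On that reading the no-data problem disappears. Because the footnote repeats the labels of d and e from an ordered list, the other reading is plausible too, so this part is conditional. The never-treated patient counted under a is doubtful in any case: section 8.3.1.2 limits CRF collection to patients with a record of at least one dose. For lost patients, section 8.9.1 plans tracing to obtain adverse-event status, but only as far as possible. That reduces the dilution without removing it.

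A reader might also take this to be the only safety output for excluded patients. It is not: section 8.7.2.1 plans separate analyses for use beyond the label, which covers f, and a description of patients lost to follow-up. For groups a to c, no other planned adverse-event output was found.

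Section 9.1 requires consent before participation, so the gap from dose to consent may be only days. That bears on the size of the effect, not on its existence. A split by exclusion reason could be made in an analysis plan that is not shown here. However, the protocol itself fixes the exclusion order, the footnote, the statistic and the collection window.

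**Conclusion.** The point holds in a limited form. By the protocol's own rules, the incidence for excluded patients mixes patients followed from first dose (f, and those in a not dosed before consent) with patients already on drug when event collection began (all of b and c, possibly some of a). It omits early on-drug events for part of its denominator and so understates incidence from first dose. The direction against a fixed 24-week window is not determined. If the footnote follows the ordered categories, patients without safety data in a to c lower the proportion further.

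The size cannot be established from the protocol. On the assumed inputs, a true 24-week figure of 20% would appear as 13.8% to 21.6% in late entrants, and dilution would take 20% to between 19% and 16%. The table is supplementary and the main safety-set incidence is not affected, so this is a minor point that is worth correcting.

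**What to change.** Keep the table, which the protocol ties to the regulator's guideline, and make three changes in section 8.7.2.1:

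1. Present it by exclusion reason instead of pooling a, b, c and f.
2. Label b and c as events after consent in patients already on treatment, and report the time from first dose to consent. Mark any group a patients dosed before consent in the same way.
3. Reword the footnote so that any excluded patient who took no JARDIANCE, or for whom no safety information exists, is left out of the denominator whichever reason he or she is first counted under.

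No new data are needed: section 8.2.3.2 already records the contract date, the consent date and the drug start date at Visit 1. The cost is a few sentences, a split of an existing table and wider intervals in the smaller groups. The guideline cited in the footnote is not at hand, so the sponsor should confirm that the new wording is compatible with it.

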8.7.3 Efficacy analysis

- Mean, standard deviation, minimum value, maximum value, and median of changes in glycosylated hemoglobin(HbA1c) and fasting plasma glucose(FPG), body weight, and blood pressure (SBP, DBP), which were measured at the last visit versus baseline, should be presented, and if there is difference before administration versus after administration should be analyzed using paired t-test.
- ② If there is difference in the change of glycosylated hemoglobin(HbA1c) according to demographic parameters mentioned in 8.7.1 should be analyzed using t-test or ANOVA(Analysis of Variance).
- The frequency and percentage of patients who had glycosylated hemoglobin(HbA1c) reaching less than 7% (target efficacy response rate) at the last visit should be calculated, and the frequency and percentage of patients with glycosylated hemoglobin(HbA1c) decreased by at least 0.5% at the last visit should be calculated.
- For final efficacy evaluation (improved, unchanged, aggravated, unassessable) and 'effective(improved)'/'ineffective(unchanged, aggravated)', the number and percentage of subjects should be mentioned. The final effectiveness evaluation of "Improved" will be classified as "Effective", "Unchanged" and "Aggravated" will be classified as "Ineffective". The effectiveness rate and its 95% confidence intervals will be estimated with exact method.
- ⑤ To estimate any factors that are thought to influence an effective ratio, logistic regression analysis should be conducted, and for statistically significant parameters, the meaning should be described.

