6.2 BACKGROUND

Type 2 diabetes mellitus (T2DM) is characterized by increased peripheral insulin resistance and an insulin-secretory defect that varies in severity leading to raised blood glucose levels.

T2DM constitutes 90% to 95% of the diabetic population with an estimated 387 million people affected worldwide. It is now a common and serious global health problem, which for most countries has evolved in association with rapid cultural and social changes, ageing populations, increasing urbanization, dietary changes, reduced physical activity and other unhealthy lifestyle and behavioural patterns. The incidence of T2DM is expected to increase to approximately 592 million patients over the next 20 years [R14-4616].

The prevalence of type 2 diabetes mellitus (T2DM) in Korea is estimated to be 7.3% (in those over 20 years of age), and it has increased about 5-fold over the past 30 years according to a report of the Korea National Health and Nutrition Examination Survey (KNHNES III, 2005) [R13-1653]. The number of patients with T2DM is expected to increase dramatically from about 3.2 million in 2011 (8.8% of the national population) to about 4.25 million (11.1%) by 2030 [R12-1019].

JARDIANCE[®] is a reversible, highly potent and selective competitive inhibitor of SGLT2 with an IC50 of 1.3 nM. It has a 5000-fold selectivity over human SGLT1 (IC50 of 6278 nM), responsible for glucose absorption in the gut. Furthermore high selectivity could be shown toward other glucose transporters (GLUTs) responsible for glucose homeostasis in the different tissues. [P11-13842]

Empagliflozin improves glycemic control in patients with type 2 diabetes mellitus by reducing renal glucose reabsorption. The amount of glucose removed by the kidney through this glucuretic mechanism is dependent upon the blood glucose concentration and GFR [P12-00692, R11-4288]. Through inhibition of SGLT2 in patients with T2DM and hyperglycemia, excess glucose is excreted in the urine.

Proprietary confidential information © 2017 Boehringer Ingelheim International GmbH or one or more of its affiliated companies

SGLT2 is highly expressed in the kidney, whereas expression in other tissues is absent or very low [P11-13842]. It is responsible as the predominant transporter for reabsorption of glucose from the glomerular filtrate back into the circulation [P12-00692]. In patients with type 2 diabetes mellitus and hyperglycaemia a higher amount of glucose is filtered and reabsorbed. [ra00656956]

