8.1 STUDY DESIGN

This is a single arm study with JARDIANCE[®].

JARDIANCE[®] will be prescribed according to the local label and at the discretion of the treating physician. Since this is a non-interventional study, the drug will not be supplied by the sponsor. Furthermore, the sponsor will not cover the expenses related to other medications taken by the patient, interventions, procedures, or diagnostic test.

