8.2.3.2 Visit 1; Baseline Visit

Upon patient enrolment, the following will be recorded on the patient's eCRF.

- Information on the site (Hospital name, Department, Physician name, Contract date)
- Visit date

Proprietary confidential information © 2017 Boehringer Ingelheim International GmbH or one or more of its affiliated companies

- Diagnosis: date of the diagnosis of T2DM, Family history of T2DM
- Inclusion / Exclusion criteria
- Informed consent form: Date of Informed consent
- Demographic data: Age, gender, pregnancy, height, smoking status
- Diabetes mellitus related complication (Retinopathy, Neuropathy, Nephropathy, Vasculopathy, etc)
- Medical history: Hypertension, Dislipidemia, Coronary artery disease, Stroke, Liver disease, Renal failure, Allergy, Nephropathy, etc (history of concomitant disease within 6 months)
- Physical examination: body weight, blood pressure (SBP, DBP)
- Renal Function: record Serum creatinine, eGFR, urin ACR if blood test result is available (the most recent data prior to baseline)
- Effectiveness endpoints: HbA1c, FPG (Lab data should be collected within 1month prior to baseline)
- Concomitant anti-hyperglycemic agent : record any anti-hyperglycemic agents have been taken prior to the baseline visit (within 1 month prior to baseline)
- Concomitant medications: record all medications have been taken at least once since one month prior to the baseline visit.
- Dose of JARDIANCE[®] given(Daily dose(Dosage/Administration), Start date)

At visit 1, the patient will be requested to contact the treating physician in the event of any adverse events noted after initiating JARDIANCE® treatment.

8.2.3.3 Visit 2; 12 weeks from Visit 1

After 12 weeks from Visit 1, the patients will return for follow-up. The followings will be noted and recorded in the eCRF.

- Visit date
- Physical examination: body weight, blood pressure (SBP, DBP)
- Any change of JARDIANCE® given(Daily dose(Dosage/Administration), Start date, Date of discontinuation or continuation, Action taken, Causality)
- Effectiveness endpoints: HbA1c, FPG
- Renal Function: record Serum creatinine, eGFR, urine ACR if blood test result is available (The most recent data since last visit, except previously entered data)
- Concomitant anti-hyperglycemic agent including new medications taken since last visit: any change in the concomitant medications (dose and dosing intervals)

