8.3.2.2 Endpoints of effectiveness

8.3.2.2.1 Main endpoint

Change from baseline in HbA1c after 12 weeks and/or 24 weeks of treatment

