8.3.3.2 Assessment of efficacy

① HbA1c:

HbA1c should be collected within 1 month prior to baseline and after 12 weeks and 24 weeks of treatment.

② Fasting Plasma Glucose (FPG):

FPG should be collected within 1 month prior to baseline and after 12 weeks and 24 weeks of treatment.

3 Body Weight:

Body weight should be collected within 1 month prior to baseline and after 12 weeks and 24 weeks of treatment.

Blood Pressure (SBP, DBP):

Blood pressure(SBP, DBP) should be collected within 1 month prior to baseline and after 12 weeks and 24 weeks of treatment.

S Final efficacy evaluation: Final efficacy evaluation should be accessed and recorded at the end of the last visit.

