8.7 DATA ANALYSIS

8.7.1 Analysis of demographic data

Demographic data and the health status of subjects for the safety evaluation will be analysed descriptively. For continuous data, mean, standard deviation, minimum value, and maximum value will be described, while for categorical data, frequency will be shown.

Parameters corresponding to demographic data are as mentioned below.

- Basic information and disease information
 Age, gender, pregnancy, body weight, smoking status, diabetes mellitus
 complications, other medical history, disease period, Family history of T2DM,
 elderly (Age ≥ 65 years), renal impairment and hepatic impairment, allergy, long
 term use(over 24 weeks)
- ② Medication information Concomitant medication, study drug administration status (total period of drug use, average of daily dose), reason for early interruption, any anti-diabetic agents

To assess the extent of preferential prescribing and the potential for channeling bias, data from the TRAJENTA® (linagliptin) rPMS will be used as a comparator. The baseline characteristics of patients starting JARDIANCE® for the first time will be compared to the baseline characteristics of patients who started TRAJENTA® for the first time. Proportions and means (SD) of the baseline characteristics will be compared using absolute standardized differences (ASD), where an ASD of at least 10% will be considered a meaningful difference. p-values will also be calculated.

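### HbA1c change is compared across non-randomised subgroups without baseline HbA1c, so a subgroup that starts higher can appear to respond better

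*Protocol*

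**What the plan says.** The main effectiveness endpoint in section 8.3.2.2.1 is "Change from baseline in HbA1c after 12 weeks and/or 24 weeks of treatment". For subgroups, section 8.7.3, item 2, states that any difference in the "change of glycosylated hemoglobin(HbA1c) according to demographic parameters mentioned in 8.7.1 should be analyzed using t-test or ANOVA(Analysis of Variance"). No covariate is named.

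The grouping factors are those of section 8.7.1. The list opens with "Age, gender, pregnancy, body weight, smoking status, diabetes mellitus" complications and goes on to disease duration, renal and hepatic impairment, long-term use and medication information, including other antidiabetic agents. Baseline HbA1c is not on it.

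Baseline HbA1c is nevertheless collected. Section 8.3.3.2 states: "HbA1c should be collected within 1 month prior to baseline and after 12 weeks and 24 weeks of treatment". The Visit 1 list in section 8.2.3.2 has the same one-month window.

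On mechanism, section 6.2 states: "The amount of glucose removed by the kidney through this glucuretic mechanism is dependent upon the blood glucose concentration and GFR".

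**The concern.** Section 8.1 states: "This is a single arm study with JARDIANCE". The groups compared in item 2 are therefore formed by patient characteristics, not by allocation. Patients who differ in disease duration, complications or background antidiabetic treatment may plausibly also differ in starting HbA1c. If the fall in HbA1c is larger from a higher start, as the stated mechanism suggests, a test on the raw change cannot separate a group that started higher from a group that responds differently at the same starting level.

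Renal impairment shows the difficulty. Section 6.2 names GFR as a second determinant of glucose removal, so kidney function may truly modify the response. Item 2 cannot tell that apart from a baseline HbA1c gap between patients with and without impairment.

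Nothing else in the protocol fills the gap. The only multivariable efficacy model is the logistic regression in 8.7.3, item 5. It models the effectiveness rate from the final efficacy evaluation, not HbA1c change, and names no covariates. Section 8.9.3 mentions confounding only in general terms. At stake are statements about which patients gain more, made on the main effectiveness endpoint.

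**Working it through.** The protocol gives no effect size, SD or power for this comparison, and section 8.5 sets N = 3,000 by regulatory requirement. There is no stated figure to reproduce.

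**Inputs from the protocol:** N = 3,000; t-test or ANOVA on change; direction of the dependence on starting glycaemia (section 6.2).

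**Assumptions, none in the protocol:** baseline SD 1.2; residual SD of change 0.8; two subgroups of 30% and 70% (900 and 2,100 patients); two-sided 5% level; slope b of change on baseline from -0.2 to -0.6; baseline gap g from 0.1 to 0.5 HbA1c points; no subgroup difference at equal baseline.

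**Formulas**

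- Baseline-driven difference: D = b × g
- SD of change = √(b² × 1.2² + 0.8²)
- SE = SD × √(1/900 + 1/2,100) = SD × 0.0398
- Rejection probability ≈ Φ(|D|/SE - 1.96); the opposite tail, at most about half a percentage point here, is left out

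**Three cases**

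- Low end, b = -0.2, g = 0.1: D = -0.02; SD = √(0.0576 + 0.64) = 0.84; SE = 0.033; |D|/SE = 0.60; rejection about 9%.
- Middle, b = -0.4, g = 0.3: D = -0.12; SD = √(0.2304 + 0.64) = 0.93; SE = 0.037; |D|/SE = 3.23; rejection about 90%.
- High end, b = -0.6, g = 0.5: D = -0.30; SD = √(0.5184 + 0.64) = 1.08; SE = 0.043; |D|/SE = 7.0; rejection over 99%.

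**Full grid at N = 3,000 (difference in points; rejection by the unadjusted test)**

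| Slope | Gap 0.1 | Gap 0.2 | Gap 0.3 | Gap 0.5 |
|---|---|---|---|---|
| -0.2 | -0.02; 9% | -0.04; 22% | -0.06; 44% | -0.10; 85% |
| -0.4 | -0.04; 19% | -0.08; 58% | -0.12; 90% | -0.20; >99% |
| -0.6 | -0.06; 29% | -0.12; 80% | -0.18; 99% | -0.30; >99% |

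Section 8.3.1.4 removes patients without efficacy data, so fewer than 3,000 may be evaluable. With an assumed 2,000 and slope -0.4, rejection is 14%, 42%, 75% and 99% across the four gaps.

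**Simulation with and without baseline as covariate (N = 3,000, 1,000 trials per row, no true difference at equal baseline)**

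| Slope | Gap | t-test rejects | ANCOVA rejects |
|---|---|---|---|
| -0.4 | 0 | 5.8% | 6.0% |
| -0.2 | 0.3 | 41.5% | 6.0% |
| -0.4 | 0.2 | 55.3% | 4.4% |
| -0.4 | 0.3 | 89.5% | 5.8% |
| -0.6 | 0.3 | 99.0% | 6.0% |

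The mean adjusted difference is within 0.002 points of zero in every row.

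**A case that points the other way.** Let two groups have stable true means 0.3 points apart, true SD 1.0, independent noise of SD 0.66 at each measurement, and the same fall of 0.7. Change now depends on baseline only through noise. The unadjusted test is sound: mean difference 0.00, rejection 4.5%. ANCOVA is not. Reliability is 1/(1 + 0.66²) = 0.70, so the noise-induced slope is about -0.30 and the adjusted difference is shifted by 0.30 × 0.3 = 0.09 points. The simulation gives +0.09 and 75.5% rejection.

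**The case against.** The strongest reply is that item 2 asks a legitimate descriptive question. If a group that starts higher falls further, that is a real observed difference. It misleads only if read as a different response at equal baseline, which item 2 does not claim. This stands, and it is why the unadjusted result should be kept.

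Second, every size above is assumed. With no gap the test behaves normally, and with a small gap the effect is modest. Some 8.7.1 factors, such as pregnancy, may split patients far more unevenly than 30/70. This stands too. Section 6.2 supports a direction only, and it concerns glucose removal by the kidney, not an HbA1c slope.

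Third, the simulation in which ANCOVA does well assumes the model under which it must do well. The counter-case shows that ANCOVA can itself be biased between non-randomised groups. A reader might infer that regression to the mean alone invalidates the planned test, and that ANCOVA should replace it. The documents do not support either step: within-group regression to the mean leaves change scores unbiased when groups have stable, different means. The argument rests on response that depends on baseline.

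Fourth, an analysis plan that is not shown could add adjusted analyses. That is possible, but the protocol itself names the test and the factors, so the choice has not been left open.

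**Conclusion.** The point holds in conditional form. Item 2 fixes an unadjusted comparison of HbA1c change across groups that need not be comparable at baseline, while the protocol describes a mechanism by which the starting level matters. A subgroup that starts higher can then appear to respond better. Under the stated assumptions the baseline-driven difference is 0.02 to 0.30 points, with rejection from about 9% to over 99% at N = 3,000, against a nominal 5%.

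A reader might go further and conclude that the subgroup results will be largely artefacts. The documents do not support that: they report no baseline HbA1c by subgroup, no slope and no SD. The effect needs both a baseline gap and a slope that reflects response rather than measurement noise alone.

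The consequence is limited. Effectiveness is the secondary objective (section 7.2), and this is a subgroup exploration within it. The primary safety objective and the overall paired t-test do not depend on it. The correction is worth making because it is cheap and concerns the main effectiveness endpoint.

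**What to change.** In section 8.7.3, item 2:

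- Keep the unadjusted HbA1c change by subgroup.
- Show mean baseline HbA1c for each subgroup beside it.
- Add a linear model (ANCOVA) of HbA1c change with the subgroup factor and baseline HbA1c, and report adjusted differences with 95% confidence intervals.
- State that both results are descriptive, because in non-randomised groups the adjusted and unadjusted comparisons answer different questions and either can mislead.

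The cost is a short protocol amendment and slightly more analysis. No new data are needed, since baseline HbA1c is already collected.
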